## **2.1. Analysis Visit Windows and Periods**

Because subjects do not always adhere to the protocol visit schedule, the following rules will be applied to assign actual visits (immunogenicity) to analysis visits. The analysis visit windows and target days for each visit are displayed in [Table 1](#). The reference day will be generally defined as:

Day of prime (Dose 1) vaccine administration if the actual visit occurs prior to the boost (Dose 2) vaccine administration.

Day of boost vaccine (Dose 2) administration if the actual visit occurs after the boost vaccine administration.

Only the analysis time points and assays that are in scope for a specific statistical analysis (e.g. Interim Analysis, Final Analysis) are to be considered when assigning assessments to analysis visit windows. If a subject has 2 or more assessments within the same interval (analysis visit window), the one closest to the target day will be used for generating tables with descriptive statistics and graphical displays presenting data per time point. If 2 assessments are equidistant from the target day within the same interval, the latest assessment will be used. All assignments will be made in chronological order.

Because the analysis of adverse events (AEs) and laboratory abnormalities will be presented per period (and not per time point), these will be assigned to the analysis period and/or phase based on [Table 2](#).

**Table 1: Analysis Visit Windows**

Time Interval (Label on Output)	Time Interval PP a (Day)	Time Interval IG b (Day)	Target Time Point (Day)
Cohorts II and III			
Prior to boost vaccination			
Day 1 (Baseline)	≤ 1	≤ 1	1
Day 15 (14 days Post-dose 1)	[14; 16]	[2; 21]	15
Day 29 (28 days Post-dose 1)	[28; 30]	[22; 42]	29
Day 57 (56 days Post-dose 1)	[56; 58]	[43; 70]	57
Day 85 (84 days Post-dose 1)	[84; 86]	[71; 98]	85
≥Day 99 (≥98 days Post-dose 1) c	NA	≥99	-
Day 365 (364 days Post-dose 1)	[335; 395]	≥ 99	365
After boost vaccination			
Day 36 (7 days Post-dose 2)	[7; 9]	[2; 14]	8
Day 64 (7 days Post-dose 2)			
Day 92 (7 days Post-dose 2)			
≥Day 106 (7 days Post-dose 2)	NA		
Day 50 (21 days Post-dose 2)	[19; 25]	[15; 101]	22
Day 78 (21 days Post-dose 2)			
Day 106 (21 days Post-dose 2)			
≥Day 120 (21 days Post-dose 2)	NA		
Day 209 (180 days Post-dose 2)	[166; 196]	[102; 196]	181
Day 237 (180 days Post-dose 2)			
Day 265 (180 days Post-dose 2)			
≥ Day 279 (180 days Post-dose 2)	NA		

Time Interval (Label on Output)	Time Interval PP a (Day)	Time Interval IG b (Day)	Target Time Point (Day)
Day 365 (364 days Post-dose 1) d	[335; 395]	≥ 224	365
Group 4			
Day 1 (Baseline)	≤ 1	≤ 1	1
Day 29 (28 days Post-dose 1)	[28; 30]	[2; 41]	29
Day 57 (56 days Post-dose 1)	[42; 72]	[42; 73]	57
Day 90 (89 days Post-dose 1)	[75; 105]	[74; 135]	90
Day 180 (179 days Post-dose 1)	[150; 210]	≥136	180

aThe analysis based on the per protocol analysis set will be restricted to data points that fall within this window (ie, protocol-defined window).

bThe analysis based on the immunogenicity analysis set will be restricted to data points that fall within this window.

cThis analysis visit is only applicable to the sensitivity analysis of subjects in Group D (ie, ≥99-day interval vaccination schedule) as shown in [Table 3](#) below. For the other analyses (ie, non-sensitivity), this will correspond to the Day 365 analysis visit.

dFor the windows after Dose 2 administration, only Day 365 window is taken with respect to the day of Dose 1 administration.

NA: Not applicable

**Note 1:** The analysis windows and target days are based on the relative day (ie, with respect to reference day [day of Dose 1 or Dose 2 administration]). The reference day of Post-dose 1 and Post-dose 2 assessments will be dates of Dose 1 and Dose 2 administration, respectively.

**Note 2:** Derivation of changes from pre-dose should be performed with respect to the reference value.

**Note 3:** Immunogenicity sample collection at 180 days post-prime visit was discontinued according to protocol amendment 3 onward. However, this was recorded for some subjects up to protocol amendment 2 or due to the study pause (late boost vaccination) and will fall within the ≥Day 99 window. If the analysis visit window contains the day of actual boost vaccination for this visit, then the assessment closest to the vaccination will be used.

**Note 4:** The same (ie, with respect to the number of days after boost vaccination) post-boost visits are labeled differently. Day 36, Day 50 and Day 209 apply only to the 28-day interval schedule, Day 64, Day 78 and Day 237 apply only to the 56-day interval schedule. Day 92, Day 106 and Day 265 apply only to the 84-day interval schedule. ≥Day 106, ≥Day 120 and ≥Day 279 apply only to the ≥99-day interval schedule.

**Note 5:** All assignments will be made in chronological order. Once an assessment is assigned to an analysis window, it will no longer be used for a later window.

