### Per Protocol Analysis Set

The per protocol analysis set includes all randomized and vaccinated subjects, who received both the prime and boost vaccinations (administered within the protocol-defined window), have at least 1 post-vaccination (ie, after the date of vaccination) evaluable immunogenicity sample, and have no major protocol violations influencing the immune response.

The primary immunogenicity analysis will be performed on the per protocol analysis set. The analysis on the immunogenicity analysis set (including those subjects who received a late boost vaccination because of the study pause) will be included as sensitivity analysis to investigate the impact on the immune response. For the sensitivity analysis, subjects will also be categorized according to the actual Ad26.ZEBOV prime/MVA-BN-Filo boost interval as shown in [Table 3](#). In all cases for subjects who received Dose 1 (ie, only prime vaccination) but not Dose 2 while still continuing their planned visit schedule, the immune response measurements after the planned but not administered Dose 2 will not be included in graphs and tables showing descriptive statistics. These measurements will however be shown in listings, together with the indication that they are not used in the analysis.

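### In the immunogenicity-set sensitivity analysis, SAP Table 1 labels some late-boosted subjects' pre-boost samples as Day 365 and takes their true one-year samples into earlier windows

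*SAP*

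**What the plan says.** **Analyses.** SAP 2.3 bases the primary immunogenicity analysis on the per protocol set, which requires a boost inside the protocol window. "The analysis on the immunogenicity analysis set (including those subjects who received a late boost vaccination because of the study pause) will be included as" a sensitivity analysis. Subjects in it are *also* regrouped by actual prime-boost interval (Groups A to D, SAP Table 3). There is therefore an IG analysis by planned schedule and another by actual interval.

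**Windows (SAP Table 1, IG column).**
- Before boost: the ≥Day 99 row and the Day 365 row both accept any day from 99, with no upper limit.
- After boost, counted from Dose 2: 7-day [2;14], 21-day [15;101], 180-day [102;196].
- After boost, counted from Dose 1: Day 365 is ≥224.
- The per protocol column limits Day 365 to [335;395] in both places.

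**Rules.** Footnote c says of the ≥Day 99 row: "This analysis visit is only applicable to the sensitivity analysis of subjects in Group D"; then, "For the other analyses (ie, non-sensitivity), this will correspond to the Day 365 analysis visit". Note 5 fills windows in chronological order: "Once an assessment is assigned to an analysis window, it will no longer be used for a later window". SAP 2.1 tabulates the sample closest to target when a window holds several. Note 3 says that 180-day post-prime sampling was stopped, but that some such samples exist, either from before that change or because the pause delayed the boost, and it places them in the ≥Day 99 row.

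**Visits.** The protocol's Time and Events Schedule (footnotes c and x) times post-boost visits from the actual boost and limits late-boosted subjects' immunogenicity sampling to humoral ELISA at selected time points.

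**The concern.** The IG set is there to bring in late-boosted subjects, but its windows work cleanly only for boosts given on time. Antibody level depends on whether the boost has been given and how long ago. A prime-only value shown under Day 365, or a one-year value removed from it, changes what that row means.

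Protocol 11.5 names Day 365 as a visit at which schedules are compared, and leaves to the SAP the handling of samples from subjects boosted out of window. SAP 6.2.1.3 plans geometric means, responder rates and reverse cumulative curves at Day 365. If the mapping rules are followed as written, the IG-set versions of these displays would mix boosted and unboosted subjects by planned schedule, and would lose one-year data in Group D.

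**Working it through.** **Inputs.** The windows, footnotes and notes are those of SAP Table 1. The one-year visit is Day 365 ± 30 (protocol Table 3). B is the study day of the boost. Late-boost dates are not in the documents, so B was scanned from 99 upwards. Scheduled post-boost draws are assumed to fall on their target days.

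**Formula.** Day relative to Dose 2 = study day − B + 1.

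**1. The plan's own labels reproduce.** The 180-day target is relative day 181, which is study day B + 180. For B = 29, 57 and 85 this gives Days 209, 237 and 265, as in Table 1. With B up to 86, a one-year draw as early as Day 335 has relative day 335 − 86 + 1 = 250. That is above 196, so it stays in Day 365. On-time boosts cause no problem at Day 365.

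**2. Pre-boost sample.** By planned schedule, with B ≥ 99, the sample drawn before the boost meets the ≥99 condition and is filed under Day 365. For B = 200, a Day 200 prime-only sample is labelled Day 365, which is 365 − 200 = 165 days early. For B = 99-334 the sample lies outside the protocol's one-year window, Days 335-395. For B ≥ 335 its timing is acceptable. In Group D it goes to the separate ≥Day 99 row.

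Few others can fill this pre-boost row. SAP 2.3 sends samples after a planned but omitted boost to listings only, and on-schedule subjects have no pre-boost sample that late.

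**3. One-year sample.** A draw on Day 365 has relative day 366 − B. Under Note 5 the earlier window takes it, both by planned schedule and in Group D:

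| One-year draw on | Kept in Day 365 | Taken by 180-day window | Taken by 21-day window |
|---|---|---|---|
| Day 335 | B = 99-139 | B = 140-234 | B = 235-321 |
| Day 365 | B = 99-169 | B = 170-264 | B = 265-351 |
| Day 395 | B = 99-199 | B = 200-294 | B = 295-381 |

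Check of the middle row: 366 − 170 = 196 and 366 − 264 = 102; 366 − 265 = 101 and 366 − 351 = 15. For B = 352-364 the sample goes to the 7-day window.

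**4. What is then tabulated.** For B = 200 the one-year draw has relative day 166. The 6-month draw, on Day 380, has relative day 181 and is on target, so the one-year value is dropped. If the 6-month draw is missing, relative day 166 is shown as the 180-day value. For B = 300 with no 21-day sample, relative day 66 is shown as the 21-day value.

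**5. Net content of Day 365 by planned schedule, one-year draw on Day 365.**
- B = 99-169: both the pre-boost and the true one-year value carry the label. If the two rows are one visit, the one-year value wins on closeness to 365.
- B = 170-334: only the unboosted value remains.

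**6. Note 3 against Table 1.** After an on-time boost, a Day 180 sample has relative day 180 − 29 + 1 = 152 (Group 1), 180 − 57 + 1 = 124 (Group 2) or 180 − 85 + 1 = 96 (Group 3). The first two fall in the 180-day IG window and the third in the 21-day IG window. None falls in ≥Day 99.

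**The case against.** The strongest reply is about scope. The primary immunogenicity analysis uses the per protocol set and its bounded windows, so it is untouched. Day 365 ELISA is exploratory, the secondary endpoint is at 21 days post boost, and no hypothesis is tested. The regrouping built for late boosts keeps Group D's pre-boost samples in their own row. All of this stands. A reader might infer that the trial's durability results are wrong; the documents do not support that.

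A second tempting inference is that one-year samples contaminate the 21-day and 180-day results. The closest-to-target rule normally prevents this, because an on-target scheduled sample wins. Loss of the one-year value is the usual outcome, and substitution needs a missing scheduled sample. The same applies to the Group 3 sample at relative day 96.

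A third reply is that the SAP already recognises the pre-boost sample: it defines a reference value on the boost date, plans a pre-boost reverse cumulative curve, and in Note 3 prefers the assessment closest to the boost. These provisions help other displays, but none removes the sample from the Day 365 row.

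Finally, *non-sensitivity* in footnote c might mean only the per protocol analysis. The ≥Day 99 row is not applicable in the per protocol column and that set has no late boosts, so the sentence would then apply to nobody. The IG Day 365 row with its ≥99 limit would still stand.

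**Conclusion.** The defect holds for exploratory Day 365 data from late-boosted subjects in the IG-set sensitivity analysis.

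- By planned schedule, prime-only samples from boosts on Days 99-334 are labelled Day 365.
- By planned schedule and in Group D, the one-year sample is taken by an earlier window for boosts from about Day 170. This cut-off moves between 140 and 200 with the date of the one-year visit. The sample is then usually lost.
- By planned schedule, boosts on about Days 170-334 leave only an unboosted value under Day 365.

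The mapping follows from the written rules. Its extent is unknown, because actual boost dates and the number of subjects affected are not given. Note 3 implies that some subjects were still unboosted at about Day 180, and protocol 3.2 says that many UK subjects were boosted late, so the affected range is plausible. The change is worth making before the tables are programmed, as a correction to a sensitivity analysis.

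**What to change.** 1. **Bound and assign by visit.** Limit both IG Day 365 windows to an interval from Dose 1, for example [335;395]. Where this overlaps a Dose 2-relative window, assign the sample by its scheduled visit (one-year, 6-month or 21-day) and not by window order. Let one draw serve two labels if it was the scheduled draw for both, with a matching exception in Note 5. Testing [335;395] first would not be enough: it would capture on-target 6-month samples (study day B + 180) for B = 155-215 and on-target 21-day samples (study day B + 21) for B = 314-374. At B = 185 the 6-month and one-year targets are the same day.
2. **Keep a pre-boost label.** In every IG analysis, report the last sample before a late boost as pre-boost, using the existing ≥Day 99 row. Delete or correct the second sentence of footnote c.
3. **Protect the 21-day visit.** Do not let a scheduled one-year or 180-day post-prime sample fill it. A cap on the window cannot do this alone: at B = 344, Day 365 is relative day 366 − 344 = 22, exactly the target. Correct Note 3 so that it covers Day 180 samples taken after an on-time boost.

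The cost is SAP wording and visit-mapping code. Some samples would move from tables to listings.

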Screening of subjects for eligibility was performed within 12 weeks before administration of the study vaccine on Day 1. The subject population will consist of healthy (on the basis of medical history, physical examination, electrocardiogram (ECG), vital signs, clinical laboratory testing, and clinical judgment) men and women aged between 18 and 65 years (inclusive), who have no prior exposure to Ebola virus (including travel to West Africa less than 1 month prior to screening) or a diagnosis of Ebola virus disease. Subjects who received a candidate Ebola vaccine or any experimental candidate Ad26- or MVA-based vaccine in the past or with known allergy or history of anaphylaxis or other serious adverse reactions to vaccines or vaccine products, including known allergy to egg, egg products and aminoglycosides will be excluded.

DOSAGE AND ADMINISTRATION

Study vaccines (Ad26.ZEBOV, MVA-BN-Filo or placebo) will be administered as 0.5-mL IM injections into the deltoid muscle. The boost vaccination should be administered in the opposite deltoid from the prime vaccination.

All subjects will receive a vaccination, according to randomization, on Day 1 (Groups 1 to 3) and on Day 29 (Group 1), Day 57 (Group 2), or Day 85 (Group 3), at the following dose levels:

- Ad26.ZEBOV: 5×10^{10} vp, supplied in a single use vial (0.5 mL extractable);
- MVA-BN-Filo: 1×10^8 Inf.U (nominal titer); target fill 1.9×10^8 Inf.U per dose (range 1.27 to 2.67×10^8 Inf.U), supplied in a single use vial (0.5 mL extractable);
- Placebo: 0.9% saline, 0.5 mL extractable.

After each vaccination, subjects will remain at the site for a total of 60 (± 15) minutes post-vaccination to monitor for the development of any acute reactions, or longer if deemed necessary by the investigator (eg, in case of grade 3 adverse events).

Criteria for postponement of vaccination at the scheduled time for vaccine administration and contraindications to boost vaccination have been defined and will be applied by the investigator.

SAFETY EVALUATIONS

All safety evaluations will be performed as specified in the [Time and Events Schedule](#). Safety will be evaluated in all subjects from the 3 cohorts.

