- ^e Subjects in France who agree to continue the long-term follow-up after Day 365 and who reach the Day 365 visit before the roll-over study VAC52150EBL4001 is opened, will have further follow-ups in the current study until they have started in the roll-over study or for an additional 12 months (whichever comes first) or discontinued earlier. These subjects will be contacted by telephone every 3 months after Day 365 (subjects will only visit the site when clinically indicated) for the collection of information on adverse events, serious adverse events, and immediate reportable events that were ongoing at the Day 365 visit, and to report and follow up on new serious adverse events, pregnancies, and immediate reportable events. Concomitant therapies are only to be recorded if given in conjunction with serious adverse events and immediate reportable events.
- ^f Day 15 visit only for subjects in Group 3 of Cohort III.
- ^g Subjects who already attended the 6-month post-prime visit (which has been replaced with the 6-month post-boost visit per protocol amendment 3) will be required to also attend the 6-month post-boost visit.
- ^h Signing of the informed consent form (ICF) needs to be done before the first study-related activity.
- ⁱ The investigators should ensure that all study enrollment criteria have been met at the end of the screening phase. Minimum criteria for the availability of documentation supporting the eligibility criteria are described in Section 17.4.
- ^j Prestudy therapies up to 30 days prior to the start of screening and previous vaccinia/smallpox vaccination at any time prior to study entry must be recorded in the case report form (CRF).
- ^k For women of childbearing potential.
- ^l For women >45 years of age with amenorrhea for less than 2 years or ≤45 years of age with amenorrhea for more than 6 months.

- ^m If a subject's clinical status changes (including available laboratory results or receipt of additional medical records) after screening so the subject no longer meets eligibility criteria, the subject should be excluded from further participation in the study.
- ⁿ After each vaccination, subjects will remain at the site for a total of 60 (\pm 15) minutes post-vaccination to monitor for the development of any acute reactions, or longer if deemed necessary by the investigator. Solicited and unsolicited adverse events emerging during the observation period at the site will be recorded in the CRF.

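### Note 3 to SAP Table 1 is wrong for subjects boosted on time: their 180-day post-prime samples are post-boost, and the sensitivity-analysis windows file them as 180-day (Groups 1 and 2) or 21-day (Group 3) post-boost values

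*SAP*

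**What the plan says.** SAP Table 1, Note 3 deals with a visit that no longer exists: "Immunogenicity sample collection at 180 days post-prime visit was discontinued according to protocol amendment 3 onward". It adds that such samples were nevertheless "recorded for some subjects up to protocol amendment 2 or due to the study pause (late boost vaccination) and will fall within the ≥Day 99" row. Two sources are named, samples taken before Amendment 3 and samples that arose from the pause, and both are sent to the same row.

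Three other statements bear on this:

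- In Table 1 the ≥Day 99 row stands in the block headed "Prior to boost vaccination".
- Footnote c says of that row: "This analysis visit is only applicable to the sensitivity analysis of subjects in Group D", the group with a prime-boost interval of 99 days or more. For all other analyses the footnote makes the row the Day 365 visit.
- SAP Section 2.1 sets the reference day as "Day of boost vaccine (Dose 2) administration if the actual visit occurs after the boost vaccine administration". Note 1 to the table repeats the rule.

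The protocol confirms that people with such samples exist. Footnote g of the Time and Events Schedule says: "Subjects who already attended the 6-month post-prime visit (which has been replaced with the 6-month post-boost visit per protocol amendment 3) will be required to" attend the 6-month post-boost visit as well.

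**The concern.** A subject boosted on schedule has had the boost well before Day 180. The sample is then a post-boost sample and cannot belong to a pre-boost row. By SAP Table 3 these subjects are also in interval categories A, B or C, not D, so footnote c excludes them a second time. Note 3 fits only samples taken before a late boost, or from subjects with no boost.

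A programmer therefore has two instructions that cannot both be followed. Under Note 3, a post-boost value enters a pre-boost row, which footnote c turns into Day 365 outside the Group D analysis. Under Section 2.1 and Note 1, the sample takes a post-boost label that depends on the vaccination schedule. In Group 3 the nominal label is 21 days post-boost, the time point of the secondary ELISA endpoint. What is at stake is a value drawn about three months after the boost appearing in a sensitivity table as the 21-day response, in one schedule and in the early-enrolled subjects only.

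**Working it through.** **Inputs**

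- On-time boost days: 29, 57 and 85 in Groups 1, 2 and 3 (Protocol synopsis, Dosage and Administration; Section 6.1), each ±1 day (Protocol Table 3).
- Dose day is Day 1 (note to SAP Table 3). The Table 1 targets of 8, 22 and 181 for 7, 21 and 180 days show that the same convention holds after the boost.
- Immunogenicity-set windows after the boost (SAP Table 1): 21 days [15;101], 180 days [102;196]. Per-protocol windows: [19;25] and [166;196].
- Allowance for the old visit: the protocol's amendment history says that Amendment 2 widened it from 15 to 30 days. I read these as ±, giving Days 165–195 and then Days 150–210.

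**Reproducing Table 1.** Study day = boost day + relative day − 1. For relative Day 22: 29+22−1 = 50, 57+22−1 = 78, 85+22−1 = 106. For relative Day 181: 209, 237, 265. All match the printed labels.

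**Nominal sample.** Relative day = visit day − boost day + 1, and days since boost = relative day − 1.

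| Group | Relative day at Day 180 | Days since boost | Immunogenicity-set label | Per-protocol label |
|---|---|---|---|---|
| 1 | 180−29+1 = 152 | 151 | 180 days | none |
| 2 | 180−57+1 = 124 | 123 | 180 days | none |
| 3 | 180−85+1 = 96 | 95 | 21 days | none |

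Using Day 181, or moving the boost by ±1 day, gives relative Days 151–154, 123–126 and 95–98. No label changes.

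**Whole allowance, Days 150–210**

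| Group | Relative days | Visits labelled 21 days | Visits labelled 180 days | Visits inside the per-protocol 180-day window |
|---|---|---|---|---|
| 1 | 122–182 | none | 150–210 | 194–210 (relative 166–182) |
| 2 | 94–154 | 150–157 | 158–210 | none |
| 3 | 66–126 | 150–185 | 186–210 | none |

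With the narrower ±15 days, Groups 1 and 2 always get the 180-day label. Group 3 gets the 21-day label on Days 165–185 and the 180-day label on Days 186–195.

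**Which sample is used.** Section 2.1 keeps the assessment closest to target. In Group 3 the stray sample is 96−22 = 74 days from target, so any 21-day sample inside the protocol's ±3 days displaces it. Against target 181, the nominal sample is 181−152 = 29 days away in Group 1 and 181−124 = 57 days away in Group 2, so a 6-month post-boost sample near its target displaces it too. The stray value is used when the proper sample is missing, lies further from target, or falls outside the window. The last can happen because protocol Table 3 allows the 6-month visit at ±30 days, up to relative Day 211, while the 180-day window stops at 196.

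**The case against.** The strongest reply is that assignment is not really in doubt. Section 2.1 and Note 1 give every post-boost sample one reference day, and Table 1 gives it one window, so Note 3 is just an over-broad explanatory sentence. That explains what was probably intended. It does not make Note 3 right, and nothing else in the SAP says that the note gives way.

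It can also be said that the labels follow a nearest-visit rule: (22+181)/2 = 101.5, exactly where the two immunogenicity-set windows meet. Relative Day 96 is 74 days from 22 and 85 from 181, so the rule works as designed, and a label that differs by schedule reflects a real difference in time since boost. This stands. It is a reason not to redraw the general windows. Raising the lower bound of the 180-day window just above 124 would in any case still admit Group 1 at relative Day 152.

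The mismatch between the upper bound of 196 and the protocol's relative Day 211 exists without any 180-day post-prime sample. It is a separate matter and adds no weight here beyond explaining when a stray value can go unopposed.

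Three stronger readings are tempting, and the documents do not support them:

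- A reader might infer that the secondary endpoint is contaminated. Its primary analysis is per protocol, and no old-visit sample reaches [19;25]; the earliest, in Group 3, is relative Day 66.
- A reader might take Group 3 visits on Days 150–185, 36 of 61 allowed days or 59%, as the share of subjects affected. It counts calendar days. Subjects are asked to come on the exact day, and no subject count is given.
- A reader might infer that every such sample should be barred from the 180-day post-boost visit. Group 1 visits on Days 194–210 fall inside the per-protocol window and are correctly labelled; a blanket bar would remove valid data from the primary immunogenicity analysis.

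**Conclusion.** Note 3 is incorrect for subjects boosted on time and conflicts with footnote c, Note 1 and the reference-day rule. Under those rules the nominal sample goes to 180 days post-boost in Groups 1 and 2 (151 and 123 days after the boost) and to 21 days post-boost in Group 3 (95 days after). At the early edge of the ±30-day allowance, Group 2 visits on Days 150–157 also take the 21-day label.

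The consequence is small. It is confined to the immunogenicity-set sensitivity analysis and arises mainly where the proper sample is missing or outside its window. The trial is descriptive, with no formal testing. The point is worth correcting because it is cheap to do so, and because this sensitivity analysis is the one the SAP uses to examine late boosts.

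Assumptions: the old allowance was symmetric, and at least some subjects with a pre-Amendment 3 sample had been boosted on time. The second is an inference from dates. Amendment 3 is dated 26 January 2016, and the vaccination halt first appears in Amendment 4 of 1 September 2016.

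**What to change.** 1. Reword Note 3 so that it covers only 180-day post-prime samples taken before a late boost, or from subjects with no boost.
2. Add one assignment rule for subjects already boosted when the sample was drawn. Keep the sample at 180 days post-boost only if its relative day lies in the per-protocol window [166;196]. Otherwise list it as Day 180 post-prime and leave it out of the 21-day and 180-day post-boost summaries and graphs.
3. Leave the general windows of Table 1 as they are.
4. State in the study report how many samples the rule moves to the listing, by group.

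The cost is one note, one programming rule and one count. The downside is that a few subjects will have a missing value instead of a substituted one at a sensitivity-analysis visit. The per-protocol tables do not change, because the rule keeps every sample that they would use.
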